- 5) **Body-impedance analysis.** To measure body fat content we will use the tetrapolar Soft Tissue Analyzer® (STA, Akern, Florence, Italy), which can perform Bio-Impedance Analysis (BIA). This technique measures the resistance in the body tissues when a 50 kHz AC electrical current is given between four electrodes. Resistance can be measured by placing two electrodes on the dorsal hand and two on the foot at the unilateral side of the body (Lukaski & Bolonchuk, 1988). Extracellular water (ECW) as a percentage of total body water (TBW) and body cell mass (BCM) will be calculated independent of weight and height.
- 6) **ECG:** A 12-leads ECG will be made in the fasting resting state during screening in order to assess cardiac conduction parameters. Heart rate on the ECG will be defined as the mean rate of 10 R-R intervals. PQ-time, QRS-time and QT-time will be calculated, QT-time will be corrected for heart rate by using the Bazett formula (C. Bazett, 2006). The cardiac vector and ECG morphology will be assessed.
- 7) **Blood pressure and heart rate (office):** Blood pressure and heart rate will be measured using an automatic oscillometric device (Dinamap®, GE Healthcare) After an acclimatization period of >5 minutes, blood pressure will be measured three times at the non-dominant arm, with the subject in a semi-recumbent position, using an appropriate cuff-size. The mean of the last 2 measurements will be used as final value (Mengden et al., 2010; Pickering et al., 2005).
- 8) **GFR** is measured by steady-state plasma iothexol concentrations measured at T=120 and T=150 as done in our previous approved protocols.

9) **ERPF** is measured by steady-state plasma PAH concentrations measured at T=120 and T=150 as done in our previous approved protocols.

10) **Filtration fraction** (GFR/ERPF) and renal vascular resistance (ERPF/mean arterial pressure) are calculated.

12) **24-hour blood pressure** is derived from Mobil-O-graph devices (24 ambulatory blood pressure monitors, The Netherlands), which will be available at both sites.

Daytime systolic blood pressure (SBP), daytime diastolic blood pressure (DBP), nighttime SBP, daytime DBP and nocturnal dipping pattern (in mmHg) are recorded.

12) sodium sensitivity is calculated as following: changes in blood pressure due to the high-sodium diet versus diet at screening (estimated based on experience/previous trials at ~165-170 mmol/day) and the effect on this parameter by ertugliflozin versus placebo.

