10. STATISTICAL ANALYSIS

Sample size calculations

The primary endpoint of the study is to investigate the modifying effects of WHO-recommended sodium intake (90 mmol per day) vs. high sodium intake (targeted at 250 mmol per day) on the effect of ertugliflozin 15 mg daily, versus placebo, on 24-hour blood pressure in overweight/obese adults with type 2 diabetes.

Based on previous studies in patients treated with SGLT2 inhibitors, we expect a change in systolic blood pressure of 6-8 mmHg during normal sodium intake (150 mmol/day) [PMID: 33318125; PMID: 23668478]. Based on our hypothesis, this effect is increased on a low-sodium intake and reduced during high-sodium intake.

We expect a difference of 4 mmHg between the placebo-controlled effects of ertugliflozin on a low- versus high-sodium diet, with a conservative SD on this difference of 8 mmHg.

A total of 34 patients completing the study provide 80% power at a two-sided alpha of 0.05, to detect a 4 mmHg difference with the indicated SD of 8 mmHg. Drop-outs will be replaced. Based on the RED study and DAPASALT study, the power needed to detect changes in eGFR and hematocrit are of sufficient magnitude and therefore we expect sufficient power for these parameters as well. The calculation is based on a paired design. The sample size was calculated using Stata-Software (v. 11.2, College station, TX, USA).

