10.1 Primary study parameter(s)

General considerations

1. All tests of differences between treatments will be conducted at a two-sided significance level of <0.05 . In general, the null hypothesis (H_0 : no difference exists between treatment with the study drug and placebo) intervention) will be tested against the hypothesis H_1 : a difference exists between treatment with the study drug and placebo), with respect to the underlying parameter of interest.
2. All variables will be expressed as mean \pm SEM when normally distributed, or –in case of non-normal distribution- be expressed as median and interquartile range (IQR). Log transformation will be applied to obtain normal distribution as appropriate for the statistical tests.

3. In case of missing data, a multiple imputation technique will be applied and compared with complete case analysis.

Analysis population

The efficacy analysis population will be based on the per protocol (PP) principle – i.e. all subjects who completed the entire treatment period using the treatment as originally allocated. Safety analysis will be performed in all patients who received one or more doses of the study medication.

Statistical analysis of study endpoints

We will use a two-way ANOVA to evaluate the main effects of diet and treatment as well as an interaction between ertugliflozin vs. placebo during high and low-sodium intake on the main outcomes. Appropriate covariates may be added to the model. Because of the crossover design of our trial, we will assess the carryover effect by including the sequence allocation as a factor in the mixed model. If a carryover effect will be detected ($p < 0.1$), only the first study period will be analysed (treating it as a parallel randomised controlled trial).

For possible confounders, we will test whether there is an association with both the dependent and independent variable ($p < 0.1$). If this is the case, this confounder will be added to the model as covariate. Since all outcome variables – primary, secondary and exploratory – are continuous, this statistical technique can be applied.

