10.2 Secondary study parameter(s)

The secondary endpoint is analysed by comparing the effects of high-sodium on blood pressure increments during placebo and ertugliflozin treatment. An ANOVA analysis will be carried out to test significance between different conditions.

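### The primary analysis is named two ways, states no participant or period term, and does not declare the diet-by-drug interaction, for which 34 participants were sized, as the primary test

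*Combined protocol and SAP*

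**What the plan says.** **Sizing (section 10, Sample size calculations; also 4.4).** The target is an interaction: "We expect a difference of 4 mmHg between the placebo-controlled effects of ertugliflozin on a low- versus high-sodium diet". The SD assumed for that contrast is 8 mmHg. The text adds that "The calculation is based on a paired design" and that "A total of 34 patients completing the study provide 80% power at a two-sided alpha of 0.05".

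**Primary analysis (section 10.1, Statistical analysis of study endpoints).** "We will use a two-way ANOVA to evaluate the main effects of diet and treatment". The same sentence goes on to include the interaction between drug and diet. The paragraph then says that sequence will be a factor in a mixed model, to assess carryover. Nothing before that sentence introduces a mixed model, and no random effect, repeated-measures structure or period term is named.

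**Null hypothesis (section 10.1, General considerations).** The only null written out, offered as a general one, is that "no difference exists between treatment with the study drug and placebo". The primary objective (2.1, 8.1.1) is modification of that effect by sodium intake.

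**Secondary analysis (section 10.2).** "An ANOVA analysis will be carried out to test significance between different conditions".

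**Outcome variable.** The objective names 24-hour blood pressure, without systolic or diastolic; the sizing refers to systolic pressure. The item on 24-hour blood pressure in section 8.3 lists daytime values and then "nighttime SBP, daytime DBP and nocturnal dipping pattern (in mmHg) are recorded"; a 24-hour mean is not in that list.

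**The concern.** The sizing and the named test assume different error terms. In the paired contrast each participant is his or her own control, so stable differences between people cancel. A plain two-way ANOVA on 34 × 4 = 136 recordings has no participant term, and those differences stay in the residual. The estimate is the same; its standard error is too large. The later mention of a mixed model hints that something better is intended, but the plan does not say so.

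Period is a separate gap. Four 20-day blocks with three 4-week washouts span 4 × 20 + 3 × 28 = 164 days. Seasonal change, habituation to the monitor or changes in diet outside the blocks could shift blood pressure over that time. The set of sequences is not stated, 34 is not a multiple of the block size of 4 (34 = 8 × 4 + 2), and drop-outs are replaced, so balance of conditions over periods is not assured.

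Finally, the ANOVA produces three tests (diet, drug, interaction), and the plan does not say which one decides the trial or on which blood pressure summary. Those choices could then be made after the data are seen.

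**Working it through.** **1. The plan's own figure.** Inputs from section 10: difference 4 mmHg, SD 8 mmHg, two-sided alpha 0.05, paired, n = 34.
- SE = 8/√34 = 1.37; noncentrality = 4/1.37 = 2.92; 33 df.
- Noncentral t power: 0.808 at n = 34 and 0.795 at n = 33. So 34 is the smallest n that gives 80%, and the figure reproduces for the paired interaction contrast.

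**2. Implied within-participant SD.** The contrast has weights +1, −1, −1, +1 over four conditions. With equal variances and equal correlations (assumed), its variance is 4σ². Hence σ = 8/2 = 4 mmHg.

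**3. Two-way ANOVA with no participant term.** The residual variance becomes σ_b² + 16, where σ_b is the between-participant SD. The reported SE is 2√((σ_b² + 16)/34) on 136 − 4 = 132 df, while the true SE of the estimate stays 1.37. The documents give no σ_b, so a range is assumed. Power for a true 4 mmHg interaction was simulated (40,000 runs for each value):

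| Assumed σ_b (mmHg) | Total SD | Reported SE | Power |
|---|---|---|---|
| 4 | 5.7 | 1.94 | about 55% |
| 6 | 7.2 | 2.47 | about 28% |
| 8 | 8.9 | 3.07 | about 9% |
| 10 | 10.8 | 3.69 | about 2% |
| 12 | 12.6 | 4.34 | about 0.3% |

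The type I error falls below 1% throughout, so the error is towards missing a real effect.

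**4. Participant in the model, period left out.** Assume a linear drift of 5 mmHg from first to last block: 0, 1.67, 3.33, 5 (mean 2.5).
- Sum of squared deviations = 2 × 2.5² + 2 × 0.833² = 13.89; divided by 3 this is 4.63.
- With the four conditions in fully random order, the drift adds 4 × 4.63 = 18.5 to the contrast variance.
- Contrast SD = √(64 + 18.5) = 9.1; SE = 9.1/√34 = 1.56; power on 33 df is about 70%.
- The result depends on the sequence set. In a balanced four-sequence Williams square the added variance is 0 or 27.8, according to how conditions are assigned to its letters, which gives power of 81% or 66%.

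**5. Participant and period both in the model.** Residual df = 136 − 1 − 33 − 3 − 3 = 96 and SE = 1.37 with balanced periods: power 0.82. The repair therefore agrees with n = 34.

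**The case against.** The best defence is that the text is terse, not wrong. The ANOVA sentence does include the interaction, so the sized contrast is in the stated model. The same paragraph refers to a mixed model because of the crossover design, and in a crossover such a model normally carries a participant effect. The sizing is explicitly paired. The drug-versus-placebo null sits under general considerations and is offered as a general form; the objectives consistently name modification by sodium as primary. All of this stands.

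It rules out several stronger readings that a reader might infer:
- That the plan tests only main effects, or formally tests only whether the drug lowers pressure. The interaction is listed, and the general null is not designated as the primary one.
- That the plan treats the 136 recordings as independent. It does not say so; it leaves the participant term unstated and uses two model names.
- That the 24-hour mean will not be collected. The list in 8.3 repeats daytime diastolic pressure, a visible slip, and the item is headed 24-hour blood pressure. Only the choice of summary measure is open.

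What the defence does not supply is a participant term, a period term or a named primary test. Even if a mixed model with participant was intended throughout, the period and primary-test gaps remain.

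**Conclusion.** The concern holds as a specification fault in the trial's primary test. The sample size is sound, and 34 is right for the paired interaction contrast. The plan does not commit to an analysis that delivers the power: one of its two model names is compatible with the sizing and the other, taken literally, is not.

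A reader might infer that the trial has almost no chance of finding a 4 mmHg interaction. The documents do not support that. The loss to between 55% and 0.3% arises only if the ANOVA is run without participant, and its size rests on assumed between-participant SDs of 4 to 12 mmHg and on equal variances and correlations. With participant in the model, power is about 81–82%.

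The period point is independent of that reading. The fall to about 70% rests on an assumed 5 mmHg linear drift and fully random order; under other sequence sets it could be nil or somewhat larger.

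**What to change.** **Section 10.1.** Replace the two-way ANOVA, and the separate mention of a mixed model, with one stated model: a linear mixed model on 24-hour mean systolic pressure, with fixed effects for drug, diet, drug-by-diet and period (four levels), and participant as the within-subject unit. Declare the single primary null as no drug-by-diet interaction, tested two-sided at 0.05 and reported with its 95% CI. Label the main effects and the other ambulatory summaries as supportive. State the set of sequences used.

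**Section 8.3.** Add the 24-hour mean systolic pressure to the listed variables.

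**Section 10.2.** Do not carry the interaction model over. This endpoint concerns the high-sodium increment over a screening recording that lies outside the four randomised periods. A within-participant comparison of high-sodium ertugliflozin with high-sodium placebo, adjusted for period, fits it. The screening recording serves as the common baseline for reporting each increment and cancels from the simple paired drug difference: (H_E − S) − (H_P − S) = H_E − H_P.

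**Cost.** Wording, and three degrees of freedom for period. The sample size stays at 34, with power of about 0.82 under the plan's own assumptions.

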After confirmation of eligibility during screening, a 24-hr blood pressure measurement as well 24-hr sodium excretion is measured prior to the dietary blocks as detailed below. This 24-hr sodium and blood pressure measurement will be crucial for hypothesis 2. Urine containers and 24-hr blood pressure meters are provided to the patient and collected after recording.

Screening	Day 0	Day 1 (offered at home of participants to reduce travel)
Medical history	X	
Physical examination	X	
Review of medication	X	
Office blood pressure	X	
Routine hematology and chemistry	X	
HbA1c	X	
Urinary dipstick	X	
Start 24-hr urine sodium collection	X	
Start 24-hr BP measurement	X	
Return 24-hr urine sodium collection		X
Return 24-hr BP measurement		X

Subsequently, 4 of the blocks of 20 days below are conducted in random order with differences in study medication (placebo versus ertugliflozin) and sodium diet (90 mmol/day versus 250 mmol/day). The washout is 4 weeks between the blocks. Please refer to the figure on page 11. Urine containers are provided to the patients.

A sodium diet is commenced (either aimed at 90 mmol/day or 250 mmol/day) and it is expected that after 10 days this is reached (+/- 20%, due to normal variation in sodium excretion). This will be assessed with two 24 hour urine collections. Subsequently, the diet is continued and treatment with the study medication commences. In the morning of day 9, 24-hour blood pressure recording starts. At the study visit at day 10 of treatment, endpoints are collected following an overnight fast of 10-hours at our clinical trial unit as indicated below. A flow chart of study activities is attached below.

Subject will arrive at Amsterdam UMC location AMC for multimetric MRI following an overnight fast. Subjects are then brought to Clinical Research Unit (CRU) location VUMC where the 24-hour urine collection is processed (in order to assess sodium

excretion and other variables of interest obtained from 24-hr urine collection). The 24-hour blood pressure recording is stopped. Two intravenous catheters will be placed in both forearms for blood sampling and for the administration of test-agents (e.g. iohexol and PAH). A total of 125 mL blood will be drawn during the day for this purpose. The renal protocol commences with measurement of GFR and effective renal plasma flow (ERPF) based on continuous infusion for 2.5.

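### The carryover rule in section 10.1 is nearly insensitive to carryover, fires by chance in about one trial in ten, and then swaps the powered paired analysis for a first-period comparison of 8–9 people per condition

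*Combined protocol and SAP*

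**What the plan says.** Section 10.1 plans an ANOVA with diet, treatment and their interaction. It then adds that, because the trial is a crossover, "we will assess the carryover effect by including the sequence allocation as a factor in the mixed model". If that test gives p<0.1, "only the first study period will be analysed (treating it as a parallel randomised controlled trial". The consequence is written as an automatic change of analysis, not as a sensitivity check. Section 10.3 analyses the exploratory variables in the way set out in 10.1, so the rule can also fire separately for each endpoint.

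The sample size text in section 10 states "We expect a difference of 4 mmHg between the placebo-controlled effects of ertugliflozin on a low- versus high-sodium diet". It takes 8 mmHg as the SD of that contrast and calls this value conservative. It concludes "A total of 34 patients completing the study provide 80% power at a two-sided alpha of 0.05", and adds "The calculation is based on a paired design". No power, between-participant SD or error rate is given for a first-period analysis.

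Sections 3 and 8.3 describe 34 participants who each pass through four single-condition blocks in random order. Section 8.3 adds "The washout is 4 weeks between the blocks", and sections 5.2 and 8.3 put 10 days of diet before each start of study drug. Section 8.2 gives block randomisation of 4. The set of sequences does not appear in the readable text; the design figure is not shown.

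**The concern.** This is the old two-stage procedure for a two-period crossover, applied to four conditions. Three things go wrong.

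- The pre-test looks in the wrong place. A sequence effect is a difference in mean level between groups of different people. Carryover shows itself mainly within people, through what the preceding block was, and no term for the preceding condition is planned.
- When the pre-test fires, three quarters of the data are dropped, and with them the pairing on which the 80% power depends.
- The pre-test and the first-period test draw on the same between-participant differences. A chance imbalance that triggers the rule can therefore carry into the test that follows.

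The primary comparison is at stake. A trial with no carryover at all would lose its planned analysis about one time in ten.

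**Working it through.** **Inputs from the documents (sections 3, 8.3, 10 and 10.1):** 34 completers; four conditions and four periods; interaction contrast 4 mmHg; SD of that contrast 8 mmHg; two-sided alpha 0.05; rule fires at p<0.1.

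**Assumptions, not in the documents:** equal variances and constant correlation across periods; no period effect; between-participant SD as stated at each step; sequence set either four Williams sequences or all 24 orders.

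**1. The plan's own figure.** Paired SE = 8/√34 = 1.37 mmHg. Noncentrality = 4/1.37 = 2.92 on 33 df. Power = 80.8%. The stated 34 and 80% are reproduced.

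**2. Implied within-participant SD.** The contrast combines four measurements, so its variance is 4σ_w². With SD 8, σ_w = 8/2 = 4 mmHg.

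**3. First period alone.** 34/4 gives cells of 9, 9, 8 and 8. SE = SD × √(1/9+1/9+1/8+1/8) = 0.687 × SD, with 30 df.

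| Total SD (assumed) | SE, mmHg | Power for 4 mmHg |
|---|---|---|
| 4 (no between-participant variance) | 2.75 | 29% |
| 8 | 5.5 | 10.9% |
| 10 | 6.9 | 8.7% |
| 12 | 8.2 | 7.6% |
| 15 | 10.3 | 6.6% |

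The first row is a ceiling obtained from the plan's own SD.

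**4. Why the sequence factor hardly sees carryover.** Everyone takes every condition once, so sequence means differ only through the last condition, whose carryover is never observed. Suppose ertugliflozin carries c mmHg into the next block. A participant with ertugliflozin last receives c once in four periods; any other participant receives it twice. The difference in means is c/4, which is 1.75 mmHg for c = 7. With between-participant SD 12, the SD of a participant's mean is √(12² + 4²/4) = 12.2 mmHg. A 17 versus 17 comparison then has SE 12.2 × √(2/17) = 4.2 mmHg. The signal is about 0.4 of a standard error. A carryover of 7 mmHg would be the whole drug effect, since section 10 expects 6–8 mmHg.

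**5. Simulation of the rule.** F test of sequence on participant means at p<0.1; if it fires, the first-period interaction test, otherwise the paired test. Within-participant SD 4; between-participant SD 8, 10, 12 and 15; 40,000 trials per setting (20,000 for the carryover rows, at SD 12).

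| Quantity | Four Williams sequences | All 24 orders |
|---|---|---|
| Fires, no carryover | about 10% | about 10% |
| Fires, 4 mmHg drug carryover | 10.5% | 10.2% |
| Fires, 7 mmHg drug carryover | 11.4% | 10.2% |
| Rejects a true null once fired | 27–30% | about 8% |
| Rejects once fired, true effect 4 mmHg | 29–32% | 10–12% |
| Overall type I error | 7.2–7.7% | 5.2–5.3% |
| Overall power | about 76% | 73–74% |

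Further runs widen the four-sequence ranges slightly, to 7.8% overall and 32% once fired. They put the 24-order figure once fired at 8–9%, and firing under 7 mmHg carryover at up to 12%.

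**6. Cross-check by arithmetic.** Power: 0.90 × 80.8% = 72.7%; adding 0.10 × 30% gives 75.7% (four sequences), and adding 0.10 × 11.5% gives 73.9% (24 orders). Type I error: 0.90 × 5% = 4.5%; adding 0.10 × 29% gives 7.4%, and adding 0.10 × 8% gives 5.3%. Both agree with the simulation.

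The two designs differ because, with four sequences, sequence and starting condition are the same grouping of people. The pre-test and the fallback test then share their noise. With 24 orders each starting condition pools six sequences, and the link is weak.

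**The case against.** **Type I error.** A reader might infer that the rule inflates the type I error seriously. That holds for four sequences only. Section 8.2 fixes the block size, not the orders, and the figure that may show them is missing from the readable text. With all 24 orders the overall error stays near 5%. This objection stands, so only the range can be claimed.

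**No test of carryover at all.** A reader might also infer this. It is too strong: a sequence mean does contain carryover from the first three conditions, diluted by averaging. Near-insensitivity is what the calculation supports.

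**Power of about 10% once the rule has fired.** The 8–11% belongs to a first-period analysis taken on its own, at an assumed total SD. Once fired under four sequences, the test rejects about as often with a true 4 mmHg effect (29–32%) as with none (27–30%), so that rejection rate is not useful power either.

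**Meaning of the first period.** Section 5.1 speaks of a first intervention phase, a wash-out and then the other medication. If the fallback meant two blocks on one drug, about 17 would be compared with 17 on the within-person diet difference. SE = 4√2 × √(2/17) = 1.94 mmHg, and power is about 52%. Sections 3 and 8.3 favour the single-block reading, but the wording in 5.1 is less clear. Even 52% is well below 80%.

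**Size of the loss.** The overall power loss is modest, at 5 to 8 percentage points. That is fair, but nothing is gained in return, because the rule barely responds to the problem it is meant to catch.

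**Conclusion.** The rule is wrong as written. Two findings are firm because they do not depend on the sequence set: it fires in about 10% of trials with no carryover, and firing removes the pairing behind the stated power.

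The rest rests on labelled assumptions. With a between-participant SD of about 11–12 mmHg, a true 7 mmHg drug carryover raises the firing rate only to about 10–12%. With a total SD of 8–12 mmHg, the standard error rises from 1.37 to 5.5–8.2 mmHg and stand-alone first-period power is about 8–11%, with 29% as the ceiling. Overall power falls from 81% to about 73–76%. Type I error is about 7.2–7.8% overall and 27–32% once fired with four Williams sequences; it is about 5% and 8–9% with all 24 orders.

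A reader might infer from this that the sample size is miscalculated or that the order of conditions was left unspecified. Neither follows. The 34 is correct for the paired analysis, and the sequence set may be in the figure that is not shown.

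**What to change.** In section 10.1, delete the p<0.1 carryover rule and the first-period fallback. State that the primary analysis always uses all four periods, in a mixed model with participant as a random effect and period, diet, drug and diet-by-drug as fixed effects. If carryover is to be examined, add a first-order term for the condition in the preceding block. Report that as a sensitivity analysis which cannot change the primary result. Apply the same to the endpoints that section 10.3 refers back to 10.1.

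This restores 80.8% power at a 5% level under the plan's own inputs, whatever the sequence set. A particular set of orders is not needed for it. The cost is SAP wording only, with no added participants, visits or procedures. The downside is that the plan then relies on the 4-week washout, with no rule that switches the analysis if carryover does occur.
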